8.6.1 Analysis of Primary Efficacy Variable

Not applicable.

8.6.2 Analysis of Secondary Efficacy Variables

8.6.2.1 Endpoints

- Incidence of suspected NEC (Stage I)
- Incidence of confirmed NEC (Stage II and higher)
- Incidence of sepsis/bacteremia
- Incidence of feeding intolerance
- Hospital Mortality (death occurred during inpatient hospitalization)
- Incidence of other neonatal complications of prematurity
 - ROP
 - IVH
 - BDP
 - Spontaneous Gastrointestinal Perforation
 - Patent ductus arteriosus requiring treatment with indomethacin, ibuprofen or surgery

The incidence rate of each outcome will be summarized separately. The secondary efficacy will be displayed by (i) dose group and BW stratum and (ii) by all BW strata combined for STP206 low dose, STP206 high dose and control group. Incidence rate of suspected NEC (stage I), confirmed NEC (stage II and higher) will be further summarized by two subgroups: gestational age at birth is less than and equal to 28 weeks, and greater than 28 weeks.

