### 10.5.2.2. *Retinopathy of Prematurity*

Ophthalmologic examinations are required for all preterm neonates for Retinopathy of Prematurity (ROP) as per NICU ROP protocols by ophthalmologists with expertise in the diagnosis of ROP, commonly using indirect ophthalmoscope after pupillary dilation.

Retinopathy of Prematurity of any stage (see [Appendix B](#) for diagnostic and staging criteria) will be assessed through ophthalmologic examinations performed by a certified pediatric ophthalmologist. Ophthalmologic assessments for ROP will be performed per NICU standard protocols.

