### 10.5.2.3. *Bronchopulmonary Dysplasia*

Assessments for bronchopulmonary dysplasia (BPD) will be performed per NICU standard protocols by the attending physician. BPD will be defined as oxygen requirement at 36 weeks post-conceptual age to keep oxygen saturation levels above 90%. BPD will be diagnosed and assessed for severity, using the criteria provided in [Appendix B](#).

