7.3 Handling of Dropouts or Missing Data

It is not anticipated that there will be a need to adjust for missing data in this study. All data for this study will be analyzed as collected on the CRF.

The study will require a minimum of nine evaluable subjects within each BW strata and dose group. If less than nine subjects complete the minimum required study treatment duration (see Section 6.2.3) and have a post dosing assessment, then replacement subjects will be enrolled to replace the original randomized subjects who do not meet the minimum required study treatment durations. The treatment assignment for the replacement subject will be the same as the original subject who needed to be replaced. Data from the subjects who are replaced will be analyzed in the ITT and Safety analysis.

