8.3.2 Intent-to-Treat (ITT) Population

The Intent-to-treat population will consist of all randomized subjects. Subjects will be analyzed according to the randomized treatment.

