8.6 Analysis of Efficacy Parameters

Descriptive summaries will consist of frequencies and percentages for categorical measures and of the number of subjects [N], mean, standard deviation [SD], median, 25th and 75th quartiles, minimum [min], and maximum [max] values for continuous measures. Descriptive summaries will be presented for each treatment group, BW strata, and all BW strata combined.

The incidence rates of the exploratory variables for those who received STP206 vs. control will be summarized and displayed.

The analyses of efficacy variables will be performed for ITT population only.

Efficacy will be displayed by (i) dose group and BW stratum and (ii) by all BW strata combined for STP206 low dose, STP206 high dose and control group.

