14.2.3.3	Incidence Rate of Sepsis, Feeding Intolerance and Antibiotic Use Across All Birth Weight Stratifications\Intent-to-treat Population
14.2.4.1	Incidence Rate of Other Complications of Prematurity by Birth Weight Stratification (2000 - 1501 g, 1500 – 1000 g):\Intent-to-Treat Population
14.2.4.2	Incidence Rate of Other Complications of Prematurity by Birth Weight Stratification (999 - 750 g, 749 – 500 g): Study\Part A\Intent-to-Treat Population
14.2.4.3	Incidence Rate of Other Complications of Prematurity Across All Birth Weight Stratifications\Intent-to-Treat Population
14.2.5.1	Hospital Mortality Rate by Birth Weight Stratification (2000 - 1501 g, 1500 – 1000 g)\Intent-to-Treat Population
14.2.5.2	Hospital Mortality Rate by Birth Weight Stratification (999 - 750 g, 749 – 500 g)\Intent-to-Treat Population
14.2.5.3	Hospital Mortality Rate Across All Birth Weight Stratifications\Intent-to-Treat Population
14.3.1.1.1	Exposure to Study Treatment by Birth Weight Stratification (2000 - 1501 g, 1500 – 1000 g)\Safety Population
14.3.1.1.2	Exposure to Study Treatment by Birth Weight Stratification (999 - 750 g, 749 – 500 g)\Safety Population

14.3.1.1.3	Exposure to Study Treatment Across All Birth Weight Stratifications\Safety Population
14.3.1.2.1	Overall TEAEs by Birth Weight Stratification (2000 - 1501 g, 1500 – 1000 g)\Safety Population
14.3.1.2.2	Overall TEAEs by Birth Weight Stratification(999 - 750 g, 749 – 500 g)\Safety Population
14.3.1.2.3	Overall TEAEs Across All Birth Weight Stratifications\Safety Population
14.3.1.2.5	Overall TEAEs by Birth Weight Stratification (2000 - 1501 g, 1500 – 1000 g) and Gestational Age Group (<= 28 Weeks, > 28 Weeks)\Safety Population
14.3.1.2.6	Overall TEAEs by Birth Weight Stratification (999 - 750 g, 749 – 500 g) and Gestational Age Group (<= 28 Weeks, > 28 Weeks)\Safety Population
14.3.1.2.7	Overall TEAEs Across All Birth Weight Stratifications and by Gestational Age Group (<= 28 Weeks, > 28 Weeks)\Safety Population
14.3.1.3.1	TEAEs by System Organ Class and Preferred Term by Birth Weight Stratification (2000 - 1501 g, 1500 – 1000 g)\Safety Population
14.3.1.3.2	TEAEs by System Organ Class and Preferred Term by Birth Weight Stratification (999 - 750 g, 749 – 500 g)\Safety Population
14.3.1.3.3	TEAEs by System Organ Class and Preferred Term Across All Birth Weight Stratifications\Safety Population

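### BPD and ROP are tabulated on all randomised infants with no rule for those who die before assessment, so an arm with more early deaths can appear to have less of both

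*SAP*

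**What the plan says.** SAP 8.6 fixes the analysis set for efficacy: "The analyses of efficacy variables will be performed for ITT population only". SAP 8.3.2 defines that set without any survival condition: "The Intent-to-treat population will consist of all randomized subjects".

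SAP 8.6.2.1 then lists suspected and confirmed NEC, sepsis, feeding intolerance, mortality and the complications of prematurity, including ROP, IVH and BPD. Its rule for display is "The incidence rate of each outcome will be summarized separately". Death enters as its own line, "Hospital Mortality (death occurred during inpatient hospitalization", with its own set of tables ending in "Hospital Mortality Rate Across All Birth Weight Stratifications" (14.2.5.1 to 14.2.5.3).

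Two of these outcomes depend on survival to an assessment.
- **BPD** (Protocol 10.5.2.3): "BPD will be defined as oxygen requirement at 36 weeks post-conceptual age to keep oxygen saturation levels above 90" per cent. Appendix B grades severity at 36 weeks or discharge, whichever is first, on top of at least 28 days of oxygen.
- **ROP** (Protocol 10.5.2.2): "Ophthalmologic assessments for ROP will be performed per NICU standard protocols", with no fixed age.

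On missing data, SAP 7.3 expects no adjustment: "All data for this study will be analyzed as collected on the CRF". Neither document contains a composite with death, a competing-event method, or a rule for infants who die before assessment. The table shells are in a separate document (SAP Section 11), so the numerator and denominator for BPD and ROP are not on view.

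**The concern.** An infant who dies before 36 weeks, or before an eye examination, has no BPD or ROP outcome. If the percentage is cases over all randomised infants, that infant is counted as free of the condition. Deaths in one arm then lower that arm's BPD and ROP rates even when the treatment does nothing to either condition. If STP206 raised early mortality, the tables would lean towards a benefit on BPD and ROP; if it lowered mortality, they would lean towards harm. If the programmer instead drops unassessed infants, the comparison is among survivors only, and randomisation no longer protects it. The SAP does not choose between the two.

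This matters more here than in many exploratory trials, for three reasons.
- Dosing ends at 34 weeks post-conceptual age or discharge (Protocol 7.1), so every death during dosing comes before the 36-week BPD assessment.
- Complications of prematurity are classified as study outcomes and not as adverse events (Protocol 12.3.1), so the efficacy tables are the main comparative display of BPD and ROP.
- Available secondary-endpoint data go to the DSMC at each review before a higher dose or lower birth weight is opened (Protocol 7.7).

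**Working it through.** The plan gives no figure to reproduce: no power, effect size, death rate or BPD rate. The check is therefore of the mechanism, under assumed inputs.

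**Notation.** Let d be the proportion who die before the outcome can be assessed. Let r be the risk of the outcome among the remaining infants, set equal in both arms so that there is no true effect.

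- All-randomised rate = (1 − d) × r
- Ratio of all-randomised rates = (1 − d_STP206) / (1 − d_control), whatever r is
- Death or outcome = d + (1 − d) × r
- Assessed-only rate = r in both arms, but only because equal r was assumed

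**BPD, with assumed deaths of 20% (STP206) v 10% (control).** The ratio is 0.80 / 0.90 = 0.89.

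| Assumed r | All-randomised rate | Difference | Death or BPD | Difference |
|---|---|---|---|---|
| 30% | 0.80 × 0.30 = 24% v 0.90 × 0.30 = 27% | −3 points | 44% v 37% | +7 points |
| 40% | 32% v 36% | −4 points | 52% v 46% | +6 points |
| 50% | 40% v 45% | −5 points | 60% v 55% | +5 points |

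The direction reverses between the two displays. Over a wider assumed range (r of 20% to 60%; deaths of 10% v 5%, 20% v 10% and 30% v 10%) the false benefit runs from 1 to 12 points. The same formulas apply to ROP, with d counting only deaths before an eye examination result; ROP found before a death is still a case.

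**NEC, with r = 10% (the background figure for VLBW infants in Protocol 5.1).** Here d counts only deaths before NEC onset.
- Deaths 10% v 5%: 9.0% v 9.5%, a shift of 0.5 points
- Deaths 20% v 10%: 8% v 9%, a shift of 1 point
- Deaths 30% v 10%: 7% v 9%, a shift of 2 points

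These are 0.2 to 0.6 of an infant in an arm of 32. With deaths of 20% v 10%, NEC or death is 28% v 19%; that 9-point gap comes from mortality, not from NEC.

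**Scale.** Eight groups of about 12 give 96 infants. At 2:1 that is 32 low dose, 32 high dose and 32 control. A shift of 3 to 5 points is 0.96 to 1.6 infants of 32. The standard error of a difference at a 40% rate is √(2 × 0.4 × 0.6 / 32), about 12 points. Within one group of 12 there are 8 active and 4 control infants, so the classification of a single infant moves a rate by 12.5 or 25 points.

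**The case against.** The strongest reply is that the non-case rule is inferred. The SAP fixes the analysis set but not the numerator and denominator for an unassessed outcome, and the shells cannot be seen. Unassessed infants might be shown as missing or left out. This stands, and it limits the claim to the natural reading. It does not remove the gap, because leaving infants out has its own problem and the SAP states neither choice.

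Second, deaths are not hidden. Hospital mortality has its own tables on the same set, in the same arm and stratum layout, and adverse events leading to death are tabulated too. This also stands: an excess would be seen. But separate totals do not show which deaths came before 36 weeks or before an eye examination, so the combined outcome cannot be rebuilt from the planned summary tables.

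Third, a reader might infer that death distorts every secondary efficacy outcome, NEC above all. The documents do not support that. Death is itself one of the listed outcomes. The routine IVH ultrasound is at 5 to 7 days of age. Signs of NEC are assessed daily in hospital, so an infant who dies without NEC is an observed non-case, and cases over all randomised is an ordinary cumulative incidence with death as a competing event.

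Fourth, the composite has costs. It mixes outcomes, and for NEC it would be driven by deaths. That is a good reason not to make it the main display.

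**Conclusion.** The gap is real for BPD and ROP and should be closed. The SAP does not say how infants who die before assessment are classified, and both available readings can mislead: one turns early deaths into apparent benefit, the other compares survivors only. With early deaths of 20% v 10% and BPD in 30% to 50% of the remaining infants, the false benefit is 3 to 5 points. Those rates are assumptions, and the size scales with them. The direction depends only on which arm has more early deaths, given equal risk among the others and an all-randomised denominator. The shift is well inside sampling error at this sample size, but it is systematic and is most likely to matter in the two lowest birth-weight strata, if early deaths concentrate there.

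A reader might go further and conclude that the plan would conceal a mortality excess or reach a wrong efficacy conclusion. Neither follows. Mortality is reported alongside, there is no primary efficacy variable (SAP 6.4.1), and all comparisons are exploratory (SAP 7.1). For NEC the planned display is sound, and the shift is about 0.5 to 2 points at a 10% rate.

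**What to change.** In SAP 8.6.2.1 and Tables 14.2.4.1 to 14.2.4.3:
- State how infants who die before assessment are classified and which denominator is used.
- Beside the component rows, add *BPD or death before 36 weeks* and *ROP or in-hospital death before an eye examination result*.
- Show BPD and ROP with the number assessed and the number who died before assessment, with a footnote that the assessed-only rate conditions on survival.

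In the NEC tables (14.2.2.x), add *confirmed NEC or in-hospital death* as a supporting row only, and keep NEC alone as the main display.

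The cost is a short SAP change and a few table rows, made before database lock. Infant-level listings of NEC, BPD, ROP and disposition are already planned, so no new data should be needed; the CRF is not in the documents, so confirm that it holds dates of death and of eye examinations. Because the composites mix outcomes, the components and the mortality tables must stay beside them.

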8.6.3 Analysis of Pharmacokinetic Variables

Not applicable.

8.6.4 Subgroup Analyses

In general, safety and efficacy data will be summarized based on BW strata and treatment group. Incidence rate of suspected NEC (stage I), confirmed NEC (stage II and higher) will be further summarized by two sub groups: gestational age at birth is less than and equal to 28 weeks, and greater than 28 weeks

8.6.5 Exploratory Analyses

Exploratory analyses are as follows:

- The incidence of suspected NEC (Stage I) in STP206-treated subjects compared to control subjects through hospital discharge
- The incidence of sepsis in STP206-treated subjects compared to control subjects through hospital discharge
- The incidence of antibiotic usage in STP206-treated subjects compared to control subjects through hospital discharge

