#### **6.3.2. Secondary Endpoints**

The secondary endpoints of the study are:

- The incidence and the severity of AEs and SAEs in STP206-treated subjects compared to control subjects from baseline through six months after the last dose of blinded study treatment
- The incidence of clinical events (NEC, sepsis/bacteremia, feeding intolerance, death, morbidity/complications of prematurity) in STP206-treated subjects compared to control subjects from baseline through hospital discharge
- The assessment of the fecal shedding of STP206 organisms in STP206-treated subjects compared to its baseline and to control subjects through the last dose of blinded study treatment

- The assessment of the changes in routine clinical parameters in STP206-treated subjects compared to control subjects at baseline through the last dose of blinded study treatment
- The assessment of the progression of standard neonatal growth parameters in STP206-treated subjects compared to control subjects through the 6-month postdosing visit.

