### 6.3.2.1. Exploratory Endpoints

Exploratory Endpoints of the study include:

- The incidence of suspected NEC (Stage I NEC) in STP206-treated subjects compared to control subjects through hospital discharge
- The incidence of suspected sepsis in STP206-treated subjects compared to control subjects through hospital discharge
- The incidence of antibiotic usage in STP206-treated subjects compared to control subjects through hospital discharge

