5.2 Changes from the Analyses Planned in the Protocol

The definition of the Intent-to-treat analysis population was changed in this SAP to include all subjects that are randomized regardless of dosing status.

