6.4.2 Secondary Efficacy Variables

The secondary efficacy variables are:

- Incidence of suspected NEC (stage I)
- Incidence of confirmed NEC (stage II and higher)
- Incidence of Feeding intolerance
- Death
- Incidence of Sepsis
- Incidence of other neonatal complications of prematurity
 - ROP
 - IVH
 - BDP
 - Spontaneous Gastrointestinal Perforation
 - Patent ductus arteriosus requiring treatment with indomethacin, ibuprofen or surgery
- Number and percent of subject with STP206 organism (STP-6, STP-11) identified
- Time to first detection of STP206 organism (STP-6, STP-11)
- Number and percent of subjects that fall in the four growth classifications 1) appropriate for gestational age (AGA), 2) small for gestational age (SGA/Head-Spared), 3) SGA/Symmetric, and 4) large for gestational age (LGA). Where AGA is defined as both body weight (g) and head circumference (cm) are between 10th Percentile and 90th Percentile according to the gender specific growth Percentile charts. SGA/Head-Spared is defined as Body Weight (g) is <10th percentile, and Head circumference (cm) is between 10th Percentile and 90th Percentile according to the gender specific growth percentile charts. SGA/Head-Symmetric is defined as Both Body Weight (g) and Head circumference (cm) are <10th Percentile according to the gender specific growth percentile charts. LGA is defined as Both Body Weight (g) and Head circumference (cm) are >90th Percentile according to the growth percentile charts.

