6.4.3 Exploratory Efficacy Variables

Additional efficacy variables are:

- The incidence of suspected NEC (Stage I NEC) in STP206-treated subjects compared to control subjects through hospital discharge
- The incidence of antibiotic usage in STP206-treated subjects compared to control subjects through hospital discharge

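### SAP 8.6.5 analyses sepsis where the protocol's exploratory endpoint is suspected sepsis, and SAP 5.2 does not declare the change

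*SAP*

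**What the plan says.** The protocol has two sepsis endpoints, both running to hospital discharge. Section 6.3.2 puts sepsis/bacteremia among the secondary clinical events: "The incidence of clinical events (NEC, sepsis/bacteremia, feeding intolerance, death, morbidity/complications of prematurity". Section 6.3.2.1 adds an exploratory endpoint, "The incidence of suspected sepsis in STP206-treated subjects compared to control subjects through hospital discharge", and the synopsis repeats it in the same words.

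The SAP treats sepsis as follows:

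- Section 6.4.2 (secondary variables): "Incidence of Sepsis".
- Section 8.6.2.1 (secondary analyses): "Incidence of sepsis/bacteremia".
- Section 6.4.3 (exploratory variables): two items only, suspected NEC and "The incidence of antibiotic usage in STP206-treated subjects compared to control subjects through hospital discharge". There is no sepsis item.
- Section 8.6.5 (exploratory analyses): three items, one of which is "The incidence of sepsis in STP206-treated subjects compared to control subjects through hospital discharge".
- Section 11: one table series for sepsis, 14.2.3.1 to 14.2.3.3, of which the last is titled "Incidence Rate of Sepsis, Feeding Intolerance and Antibiotic Use Across All Birth Weight Stratifications". Two sepsis listings, 16.2.6.2.1 and 16.2.6.2.2, cover cultures and the Gram bacilli result.
- Section 8.7.3: blood cultures taken when sepsis is suspected during dosing go to a listing.
- Section 5.2 (changes from the protocol's analyses): one entry, beginning "The definition of the Intent-to-treat analysis population was changed in this SAP".

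**The concern.** The exploratory sentence in SAP 8.6.5 is the protocol's sentence with one word removed, and that word is what separates the exploratory endpoint from the secondary one. A programmer following the SAP text would summarise sepsis, which is already a secondary outcome, and would have no instruction to count suspected sepsis by treatment group.

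The two events are not interchangeable in this protocol. Under sections 10.3.5.1 and 10.8.2, suspicion of sepsis starts a work-up, prompts cultures and leads to temporary suspension of study drug, whatever the cultures later show. The endpoint therefore bears on the tolerability of, and exposure to, a live bacterial product. What is at stake is a protocol-listed comparison missing from the study report without explanation.

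**Working it through.** No arithmetic underlies the point itself. The check is a comparison of texts.

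**Step 1. Match the exploratory lists item by item.**

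| Protocol 6.3.2.1 | SAP 6.4.3 | SAP 8.6.5 |
|---|---|---|
| Suspected NEC (Stage I) | Suspected NEC (Stage I) | Suspected NEC (Stage I) |
| Suspected sepsis | absent | Sepsis |
| Antibiotic usage | Antibiotic usage | Antibiotic usage |

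Two of the three items carry over intact. The sepsis item is missing from one SAP list and altered in the other, so the two SAP lists also disagree with each other. SAP 8.6.5 keeps *suspected* for NEC in the bullet directly above, so the qualifier was lost from the sepsis item alone.

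**Step 2. Ask whether the altered item adds anything.** Sepsis is already in SAP 6.4.2, and sepsis/bacteremia in 8.6.2.1. The protocol's secondary endpoint has the same time limit, hospital discharge. The wording is not identical, but in substance the 8.6.5 item repeats an outcome already planned.

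**Step 3. Look for suspected sepsis elsewhere in the SAP.** It appears only in 8.7.3, as the trigger for blood cultures, with output to a listing. A listing of cultures is not an incidence by treatment group. Section 8.7.3 also describes cultures at NICU admission and during dosing. Dosing stops at 34 weeks post-conceptual age or discharge, whichever is first, so an infant still in hospital after the last dose has endpoint time that 8.7.3 does not describe.

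**Step 4. Check whether the change is declared.** Protocol 13.2.3 requires changes to planned analyses to be described and justified in the SAP, and 13.2.5 requires deviations from the protocol-defined analysis to be documented there. SAP 5.2 declares the ITT change only.

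**Step 5. Check whether a case definition exists.** Protocol Appendix B gives criteria for NEC, ROP, BPD and IVH, and none for sepsis. Neither document separates suspected from confirmed sepsis. Protocol 10.6.2 recognises clinical sepsis with negative cultures, so the unqualified word does not necessarily mean culture-confirmed.

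**Step 6. Size of the comparison affected.** Each of the eight groups nominally has 12 subjects randomized 2:1, so 12 × 2/3 = 8 on STP206 and 12 × 1/3 = 4 on control. Across the four strata that is 4 × 8 = 32 on low dose and 4 × 8 = 32 on high dose. Pooled control is 8 × 4 = 32.

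**The case against.** The strongest opposing case is that this is a wording mismatch with little consequence. Several parts of it stand.

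- **A reader might infer that suspected sepsis is never reported.** The documents do not support that. Cultures from suspected cases are listed, the table shells are in a separate document that is not available here, and SAP 11 allows further tables. The supportable statement is that the SAP text names no incidence summary.
- **Table titles prove little.** The 14.2.2 series is titled for NEC alone, although 8.6.2.1 requires suspected and confirmed NEC in it. The word sepsis in a title does not by itself exclude a row for suspected cases.
- **Repetition across tiers is not unusual in this SAP.** Suspected NEC is both secondary and exploratory, so the duplication alone does not show an error. The missing qualifier does.
- **The protocol is not uniform either.** Its efficacy analysis list (13.2.3.1) has sepsis, not suspected sepsis, and leaves details to the SAP. The SAP thus agrees with 13.2.3.1 and departs from 6.3.2.1. This may explain the omission, but it does not remove an endpoint that the protocol lists twice.
- **A reader might infer that suspected sepsis is the more frequent and more informative safety signal.** Neither document gives a rate. If any work-up counts as a case, suspected cases include by construction every sepsis case found through that work-up. But a work-up count is also less specific, and calling it more informative is judgement. The stopping events in protocol 7.1.1 do not include it.

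Two possible substitutes do not fill the gap. Antibiotic usage also captures empiric treatment after birth (10.6.2) and treatment for feeding intolerance (10.5.1.1). Adverse event tables are uncertain because late onset sepsis is listed as a complication of prematurity (10.5.2.5), and complications are not classified as AEs (12.3.1), while 10.3.5.1 makes any sepsis an SAE.

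**Conclusion.** The mismatch is confirmed and undeclared. One of the three exploratory endpoints in protocol 6.3.2.1 has no incidence summary planned in the SAP text, and the item in its place in 8.6.5 in substance repeats a secondary outcome. This is an incorrect analysis specification, not merely missing detail.

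The consequence is small. Protocol 13.2.1 and SAP 7.1 make all comparisons exploratory, the sample size was not set statistically, and the affected comparison is descriptive, with nominally 32 subjects in each pooled arm. No confirmatory conclusion depends on it.

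The conclusion assumes that the unseen shells do not already contain a suspected-sepsis row. If they do, only the SAP text needs to be corrected. It does not depend on any assumed rate of suspected or confirmed sepsis.

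**What to change.** Before database lock:

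1. Restore *suspected* in the sepsis item of SAP 8.6.5, and add a matching bullet to 6.4.3, which at present has no sepsis item to edit.
2. Give an analysis definition. One option is a subject for whom a work-up for suspected sepsis was started under protocol 10.3.5.1, whatever the culture result, with confirmed cases stated to be a subset so that the overlap between rows is explicit. This definition is a proposal; the documents contain none.
3. Check that the CRF captures such work-ups through hospital discharge and not only during dosing. The listing titles suggest that culture data are collected, but no CRF is available to confirm it.
4. Add a row to tables 14.2.3.1 to 14.2.3.3, separate from sepsis/bacteremia.

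If the endpoint was dropped on purpose, state and justify that in SAP 5.2 instead, and remove the duplicate item from 8.6.5.

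The cost is one definition and one table row, plus the CRF check. If work-ups after dosing were not captured, the SAP should state the shorter period that the data can support and declare it in 5.2.
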